5. STUDY POPULATION SUMMARY

5.1. General

The ITT population (ie, randomized population) will be used for all study population summaries unless otherwise noted. Summaries of the efficacy endpoints will be presented by treatment group and overall for CM and EM patients respectively, and total unless otherwise noted. Summaries of the safety endpoints will be presented by treatment group and overall for combined EM and CM patients.

The FAS will be used for all efficacy analyses. Summaries for the FAS population will be presented by treatment group, new patients and placebo-treated rollover patients, active rollover patients, and overall for CM and EM patients.

The safety population will be used for all safety analyses. Summaries for safety population will be presented by treatment group (loading dose of TEV 48125 at 675 mg followed by monthly TEV-48125 at 225 mg, monthly TEV-48125 at 225 mg, and quarterly TEV-48125 at 675 mg) and overall. EM and CM patients will be combined for the safety analysis.

For continuous variables, descriptive statistics (n, mean, SD, SE, median, minimum, and maximum) will be provided. For categorical variables, patient counts and percentages will be provided. Categories for missing data will be presented if necessary.

For the rollover patients, their baseline data refer to the baseline in the pivotal studies.

5.2. Patient Disposition

Patients screened, screening failures, and the reasons of the patients not randomized will be summarized only for the newly enrolled patients using patient counts.

The numbers of patients randomized (ITT population), patients randomized but not treated, patients in the safety population, and FAS, patients who completed the study, and patients who discontinued from the study will be summarized using descriptive statistics by indication (EM or CM) and overall for new randomized patients and rollover patients separately. The number of patients discontinued from the study will also be summarized using descriptive statistics by reasons for withdrawal. The denominator for calculating the percentages will be the number of patients in ITT population.

The disposition table will also be presented by treatment group, new patients and placebo-treated rollover patients, TEV-48125-treated rollover patients, and overall for CM and EM patients respectively for ITT population.

5.3. Demographics and Baseline Characteristics

The demographics and baseline characteristics including age, sex, race, ethnicity, country, region, weight, height, body mass index, years of migraine, concomitant preventive medication use for migraine, use of topiramite or onabotulinumtoxinA for migraine in the past, and any triptans/ergots during baseline will be summarized for the ITT population, FAS, safety population and ADA analysis set.

The baseline e-diary efficacy variables listed in Section 4.2, and the baseline scores for the assessments of migraine impairment and quality of life including HIT-6 for CM patients, MIDAS for EM patients, MSQOL, EQ-5D-5L measurements, PHQ-9, and WPAI will be summarized.

5.4. Medical History

All medical history will be coded using the Medical Dictionary for Regulatory Activities (MedDRA) version 18.1. The incidence of medical history will be summarized by system organ class (SOC) and preferred term (PT). Patients are counted only once in each SOC and only once in each PT.

5.5. Prior Medications or Therapy

For the rollover patients, their prior medications refer to the medication before they took the 1st study drugs in the pivotal studies.

All prior medications or therapy will be coded using the World Health Organization dictionary of medical codes (WHO Drug) version 01 March 2015. The incidence of prior medications or therapy will be summarized using descriptive statistics by therapeutic class and PT. Patients are counted only once in each therapeutic class category, and only once in each PT category. Prior medications will include all medications taken prior to the first study drug treatment.

The subset of prior medications will be summarized for the following categories:

- triptans and ergots
- nonsteroidal anti-inflammatory drugs (NSAIDs) for migraine/headache
- NSAIDs for reasons other than migraine/headache
- opioids for migraine/headache
- opioids for reasons other than migraine/headache
- other

5.6. Physical Examinations

Physical examinations results will be listed. Patients with at least 1 abnormal finding (overall) and abnormal findings for each category will be summarized.

5.7. Electrocardiography

ECG findings (normal, abnormal, and missing) at baseline will be summarized using descriptive statistics.

5.8. Childbearing Potential

All patients must be of nonchildbearing potential as defined in protocol Section 4.1. Information related to childbearing potential will be collected and listed.

6. EFFICACY ANALYSIS

6.1. General

The FAS will be used for all efficacy analyses. The patients with CM and patients with EM will be summarized separately for their efficacy endpoints. The descriptive statistics will be presented by treatment group and visits/months for new patients and placebo-treated rollover patients, TEV-48125-treated rollover patients, and overall under the same treatment, unless otherwise specified.

Efficacy endpoints will be derived from headache related question responses (eg, occurrence of headache, duration of headache in each day, maximum severity of headache, and acute migraine-specific medication use etc. [Appendix A](#)) collected daily using an electronic headache diary device for month 1, 2, 3, 6 and 12.

Following the Classification Committee of the International Headache Society guidelines ([Silberstein et al 2008](#)), headache days of at least moderate severity for both CM and EM patients will be defined for the purpose of this study as a calendar day (0:00 to 23:59) when the patient reports:

- a day with headache pain that lasts ≥ 4 hours with a peak severity of at least moderate severity
- or
- a day when the patient used an acute migraine-specific medication (triptans or ergots) to treat a headache of any severity or duration

Migraine day is endorsed based on the same criteria as described in the pivotal studies. For CM patients, a migraine day is endorsed when at least 1 of the following situations occur:

- a calendar day (0:00 to 23:59) demonstrating ≥ 4 consecutive hours of a headache meeting criteria for migraine with or without aura
- a calendar day (0:00 to 23:59) demonstrating ≥ 4 consecutive hours of a headache meeting criteria for probable migraine, a migraine subtype where only 1 migraine criterion is missing
- a calendar day (0:00 to 23:59) demonstrating a headache of any duration that was treated with migraine-specific medications (triptans and ergot compounds)

For EM patients, a migraine day is endorsed when at least 1 of the following situations occur:

- a calendar day (0:00 to 23:59) demonstrating ≥ 2 consecutive hours of a headache meeting criteria for migraine with or without aura
- a calendar day (0:00 to 23:59) demonstrating ≥ 2 consecutive hours of a headache meeting criteria for probable migraine, a migraine subtype where only 1 migraine criterion is missing
- a calendar day (0:00 to 23:59) demonstrating a headache of any duration that was treated with migraine-specific medications (triptans and ergot compounds)

The derivation logic is presented in [Appendix B](#).

In addition, the following questionnaires will be used for the assessments of migraine impairment, quality of life and satisfaction of treatment etc. during the study (See [Table 1](#) and [Table 2](#) for the schedules of the assessments).

- assessment of headache impact in patients with CM using the HIT-6 ([Appendix C](#))
- assessment of headache-related disability based on lost days of activity in 3 domains (work, household work, and nonwork) over the previous 3 months in patients with EM using the MIDAS ([Appendix D](#))
- quality of life, as measured by the MSQOL questionnaire ([Appendix E](#))
- health status, as measured by the EQ-5D-5L questionnaire ([Appendix G](#))
- assessment of patient satisfaction, as measured by the PGIC scale, at 4 weeks after administration of the 1st dose, 3rd dose, 6th dose, 9th dose, and last (12th) dose of study drug ([Appendix H](#))
- patient depression status, as measured by the PHQ-2 and the 9-item PHQ-9 ([Appendix I](#))
- patient work productivity and activity impairment, as measured by the WPAI questionnaire ([Appendix J](#))

The **monthly average** number of days of efficacy variables **during a 4-week period** after each dose at visits 2, 3, 4, 7, and 13 will be derived and normalized to **28** days equivalent for month 1, 2, 3, 6 and 12, respectively, using the following formula, where the monthly data separated by each visit will be used.

$$\frac{\sum \text{Days of efficacy variable during the 4 week period}}{\sum \text{Days with assessments recorded in the eDiary for the 4 week period}} \times 28 \quad (1)$$

The **baseline values** for the patients rolling over from the pivotal Studies TV48125-CNS-30049 and TV48125-CNS-30050 will be carried forward. The **baseline value** for the eligible new randomized patients will be calculated using all data collected in the run-in period, ie,

$$\frac{\sum \text{Days of efficacy variable during the run – in period}}{\sum \text{Days with assessments recorded in the eDiary for the run – in period}} \times 28 \quad (2)$$

The **percentage of reduction** in the monthly average number of an efficacy variable will be calculated as

$$\frac{\text{baseline value} - \text{postbaseline value}}{\text{baseline value}} \times 100\% \quad (3)$$

where the postbaseline value in the equation is calculated by formula (1) for the variables **during the 4-week period** after each dose at visits 2, 3, 4, 7, and 13 for months 1, 2, 3, 6, and 12, respectively.

6.2. Primary Efficacy Variable(s) and Analysis

There is no primary efficacy endpoint and analysis.

6.3. Secondary Efficacy Variable(s) and Analysis

There are no secondary efficacy endpoints.

6.4. Exploratory Efficacy Variables and Analysis

The exploratory efficacy endpoints are listed in Section 2.2.3.

6.4.1. Variable Definition

6.4.1.1. Headache Diary Data

The exploratory efficacy variables derived from the headache e-diary data include mean change from baseline in the monthly average number of migraine days, headache days of at least moderate severity, headache days of any severity, days of use of any acute headache medications, headache hours of at least moderate severity, headache hours of any severity, days with nausea or vomiting, days with photophobia and phonophobia *during the 4-week periods* after visits 2, 3, 4, 7, and 13 for months 1, 2, 3, 6, and 12. The change from baseline is calculated as *postbaseline value – baseline value*, where the postbaseline values are derived using formula (1) in Section 6.1 and the baseline values are carried forward from the pivotal studies or calculated using formula (2) in Section 6.1 for new patients

If a patient has missing days of entries in the e-diary for a month, his/her monthly average number of days of study variables *during the 4-week period* for that month will be handled as discussed in Section 4.5.

The percent reduction in the monthly average number of migraine days *during the 4-week period* after each dose at visits 2, 3, 4, 7, and 13 for months 1, 2, 3, 6, and 12 will be calculated by formula (3) in Section 6.1. The patient is considered as a responder reaching 50%, 75%, or 100% reduction if his/her percent reduction is 50% or more, 75% or more, or 100%, respectively. Similar definition will be applied to calculate the proportion of patients reaching at least 50%, 75%, or 100% reduction in the monthly average number of headache days of at least moderate severity during the 4-week period for months 1, 2, 3, 6 and 12. If a patient is early discontinued from the study, he/she will be counted as a non-responder.

If a patient has 50% reduction or more in monthly average number of migraine days during month 3, he/she will be considered a responder during the 4-week period after visit 4. In addition if the patient also has 50% reduction or more during the 4-week periods after visits 7 and 13, he/she is a responder for months 6 and 12, respectively, and the level of effect is sustained after visits 7 and 13. Similar definition will be applied to calculate the proportion of patients reaching at least 75% (and 100%) reduction in the number of migraine days during the 4-week period after visits 4, 7, and 13 for whom this level of effect is sustained through month 12. The proportion of patients reaching at least 50%, 75% and 100% reduction in the number of headache days of at least moderate severity during the 4-week period after visits 4, 7, and 13 for whom this level of effect is sustained throughout the 12-month period after visits 4, 7, and 13 will be derived similarly.

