3.14.4. Procedures After Study Drug Treatment

3.14.4.1. Patients Rolling Over from the Pivotal Efficacy Studies and New Patients (Final Visit [Visit 15 (Day 533)])

Procedures after study drug treatment will be the same for patients rolling over from the pivotal efficacy studies who receive study drug during the current study and patients not rolling over from the pivotal efficacy studies.

Patients who participate in the study in compliance with the protocol for the entire treatment period (ie, from visit 2 through visit 14) will be considered to have completed the study. Patients may be treated with standard of care following completion of visit 14.

Patients who complete the treatment period will have a follow-up visit approximately 7.5 months (225 days [the approximate equivalent of 5 half-lives]) after administration of the final dose of study drug. The following procedures/assessments will be performed at this visit:

- Inquire about adverse events.
- Inquire about/review concomitant medications.
- Perform physical examination (including weight).
- Complete the eC-SSRS Since Last Visit version.
- Obtain a 4-mL blood sample for plasma TEV-48125 concentration determination.
- Obtain a 5-mL blood sample for serum ADA assessment.
- Obtain a 5-mL urine sample for biomarker analysis.
- Obtain an 18.5-mL blood sample (6 mL each for serum and plasma and 6.5 mL for RNA) for serum, plasma, and RNA biomarker analysis.

In addition, a single 6-mL blood sample for pharmacogenomics (DNA) may be obtained from patients who consent to pharmacogenomics analysis if the sample is not obtained at an earlier visit.

Patients who discontinue treatment prematurely must be encouraged to continue to attend the regular scheduled visits, and complete the prescribed safety and efficacy evaluations through the EOT visit and the follow-up visit, if at all possible.

Patients who both discontinue treatment and also withdraw from the study should have EOT (early withdrawal) visit procedures/assessments (see [Table 1](#) and [Table 2](#)) performed on the last day the patient receives the study drug, or as soon as possible thereafter. The patient should also return for the follow-up visit approximately 7.5 months after the last dose of study drug if at all possible.

Procedures for patients who withdraw prematurely from the study are described in [Section 4.4](#). As appropriate, patients should be treated with standard of care following termination of the study.

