2.3. Sample Size and Power Considerations

There are no statistical considerations for this sample size. A total of 1842 patients (867 patients from Study TV48125-CNS-30049, 675 patients from Study TV48125-30050, and approximately 300 patients who did not participate in the pivotal efficacy studies) are planned for enrollment, and a 30% drop-out rate is anticipated.

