2.5. Sequence of Planned Analyses

2.5.1. Interim Analyses

In support of a biologics license application (BLA), a cut-off date will be determined for this study and all data accumulated up to the cut-off date will be analyzed. An interim CSR will be prepared on the interim data.

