3.3. Full Analysis Set

The full analysis set (FAS) will include all patients in the safety population and have at least 10 days of efficacy assessments by e-diary post the 1st injection for this study.

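### The non-responder rule for early discontinuers in SAP 6.4.1.1 has no time limit, so read literally it overrides responses observed before the patient left

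*SAP*

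**What the plan says.** The responder paragraph of SAP 6.4.1.1 defines 50%, 75% and 100% responders in migraine days by month. It extends this to "headache days of at least moderate severity during the 4-week period for months 1, 2, 3, 6 and 12" and closes with: "If a patient is early discontinued from the study, he/she will be counted as a non-responder".

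Three other places bear on the point:

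- The following paragraph of 6.4.1.1, which leads into sustained response, says: "If a patient has 50% reduction or more in monthly average number of migraine days during month 3, he/she will be considered a responder". It sets no condition on staying in the study afterwards.
- SAP 4.5 works month by month. A month with 10 or more diary days is prorated to 28 days and used; a month with fewer is missing.
- SAP 3.3 limits the full analysis set to treated patients who "have at least 10 days of efficacy assessments by e-diary post the 1st injection for this study".

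On drop-out, SAP 2.3 says that 1842 patients "are planned for enrollment, and a 30% drop-out rate is anticipated", with no time frame. On the interim cut for the licence application, SAP 2.5.1 says that "all data accumulated up to the cut-off date will be analyzed". It gives no responder denominator and no rule for patients still on treatment who have not reached a given month.

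**The concern.** A responder rate for a 4-week period should depend on what happened in that period. An undated non-responder rule makes the month-1 or month-3 rate depend on drop-out that occurs months later, and it discards valid diary data that the mean-change tables would still use. The loss is greatest at the early months and nil at month 12, so the rule would flatten the time profile and could hide a decline in response. Two programmers could both follow the SAP and produce different responder tables.

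At the interim cut there is a separate gap. A discontinuer already has a defined month-12 status, non-responder, while a patient with the same entry date who is still on treatment has none. Unless the denominator is fixed in advance, the two could enter the month-12 table at different times.

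**Working it through.** **1. One patient, three rules.** Take a patient with a complete month-3 diary and a 60% reduction in migraine days who leaves the study in month 8.

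| Rule | Month-3 result |
|---|---|
| SAP 6.4.1.1, closing sentence of the responder paragraph, read literally | non-responder |
| SAP 6.4.1.1, following paragraph | responder |
| SAP 4.5 | month 3 is valid and used as observed |

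Nothing in the SAP says which governs.

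**2. The plan's own figures.** SAP 2.3: 867 + 675 + 300 = 1842, which reproduces. A 30% drop-out is 0.30 × 1842 ≈ 553 patients. There is no power calculation or planned responder rate to reproduce.

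**3. Size of the literal rule.** The 30% is from SAP 2.3. Month ends at days 28, 56, 84, 168 and 336 follow from the visit schedule. Two inputs are assumptions: drop-out is even over 336 days, and a share *q* of the later leavers had responded in the month concerned.

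- Share leaving after a month that ends on day *e*: 0.30 × (336 − *e*)/336.
- Fall in that month's rate under the literal rule: that share × *q*.

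For month 3: 0.30 × (336 − 84)/336 = 0.225, about 414 of 1842 patients. At *q* = 20% the fall is 0.225 × 0.20 = 4.5 points.

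| Month (ends day) | Leave later | Fall at q = 0% | q = 20% | q = 50% |
|---|---|---|---|---|
| 1 (28) | 27.5% | 0 | 5.5 points | 13.75 points |
| 2 (56) | 25.0% | 0 | 5.0 | 12.5 |
| 3 (84) | 22.5% | 0 | 4.5 | 11.25 |
| 6 (168) | 15.0% | 0 | 3.0 | 7.5 |
| 12 (336) | 0% | 0 | 0 | 0 |

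The drop-out pattern matters little. With a constant hazard, the share still in the study at day 84 is 0.70^(84/336) = 0.915. The share leaving later is then 0.215, and the month-3 fall is 4.3 points at *q* = 20% and 10.7 at *q* = 50%.

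The 10-day condition for the full analysis set also changes little: under even drop-out it removes about 0.30 × 10/336 = 0.9% of patients.

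**4. Interim cut, as an illustration only.** Assume uniform entry over 364 days, a cut at day 420, 30% drop-out at constant hazard, and 50% response among month-12 completers. At the cut there are 298 month-12 completers and 389 discontinuers.

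- Discontinuers counted at once, ongoing patients missing: 0.50 × 298/(298 + 389) = 21.7%.
- Only patients who entered at least 336 days before the cut: 0.50 × 0.70 = 35.0%, the same as the final rate.

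Both figures count discontinuers as non-responders. The difference comes wholly from who is in the denominator.

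**The case against.** The strongest reply is that the sentence is ordinary non-responder imputation for months that a discontinuer cannot supply. Responder status in the same paragraph is defined period by period, and the next paragraph takes month-3 response from month-3 data. That reading is plausible and may be what was meant. For this reason the documents do not support saying outright that early responses will be erased, or that the sustained-response analysis starts from a wrong month-3 set. What stands is that the sentence, as written, says something else, and nothing resolves the conflict.

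The size also rests on inputs outside the documents. The 30% has no time frame, and the study includes about 6.5 months of follow-up after treatment. Protocol 3.14.4.1 treats patients who finish the treatment period as completers, so later losses should not trigger the rule. Protocol 3.12 lists lack of efficacy among the reasons for leaving, so response among leavers could be low; at 0% there is no effect. Patients who stop treatment but stay in the study are not covered by the rule.

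The consequence is limited. All efficacy endpoints are exploratory, no testing is planned, the primary objective is safety, and the mean-change summaries are untouched. Any bias in the monthly rates is downward, so it does not flatter the drug.

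A reader might also infer that the same rule drives down the interim month-12 rate. The documents do not support that. SAP 2.5.1 does not say that discontinuers enter the denominator while ongoing patients are left out. With a denominator of patients due for month 12, the rule produces no interim fall.

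**Conclusion.** The concern holds as an undated rule that conflicts with its neighbouring paragraph and with SAP 4.5. Followed literally, it overrides valid responses at months 1, 2, 3 and 6 for patients who leave later. At month 3 the fall is between 0 and about 11 points for response among later leavers of 0% to 50%, and 4.5 points at 20%, if the 30% drop-out falls evenly within 336 days. The final month-12 rate does not change.

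The missing interim denominator is a separate omission; time-limiting the discontinuation rule would not cure it.

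The SAP should be corrected before the responder tables are programmed, but neither issue bears on the safety conclusions.

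**What to change.** Replace the closing sentence of the responder paragraph in SAP 6.4.1.1 with:

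*A month with at least 10 observed e-diary days is analysed as observed, including the month in which the patient discontinues. A patient who discontinues early is counted as a non-responder only for the months on or after discontinuation that have fewer than 10 e-diary days.*

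Putting the 10-day test first gives one answer for the month of departure. State that the same rule applies to the sustained-response endpoint in the following paragraph.

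Add to SAP 2.5.1:

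*For each month, the interim responder denominator is limited to patients whose first-dose date makes that month's planned 28-day window due to end by the cut-off date.*

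The planned window is needed because SAP 4.6 ends a month at the next dose, which a discontinuer does not have. With this limit, discontinuers do not enter the month-12 table ahead of ongoing patients with the same entry date.

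The cost is a short SAP amendment and the matching programming. No new data are needed.
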